8. CORRELATIVE BIOMARKER STUDIES

8.1 Biomarkers Program

The exploratory biomarkers program will include the following sample collection and tests as detailed in the Lab Manual. Frozen samples will be kept at the laboratories of Weill Cornell Medical College where they will be analyzed.

8.1.1 MRD analysis for molecular responses

Whole blood in 10mL purple-top tubes will be collected at baseline, after cycles 6 and 12 of induction, and every 4 cycles for year 2, and every 6 cycles for years 3-5 during maintenance.

8.1.2 Cell-free DNA and soluble plasma cytokine/biomarkers

Whole blood in 10mL purple-top tubes will be collected for cytokine studies at baseline, weekly for cycle 1, on C2D1, C4D1, and C6D1, then following the same frequency as the MRD collection and at time of progression. Cell-free DNA (cfDNA) will be collected in Streck tubes at baseline and MRD time points. Additionally, one-time buccal swab / saliva sample collection for germline control should occur at screening, on treatment or off treatment. [name], Professor of hematopathology at the Donald and Barbara Zucker School of Medicine at Hofstra/Northwell will serve as an external investigator for cell-free DNA study analysis.

8.1.3 Circulating immune cells

Whole blood in 10mL purple-top tube will be collected at baseline, weekly for cycle 1, then on C2D1, C4D1, C6D1, and time of progression, and subject to real-time flow cytometric analysis of peripheral blood mononuclear cells (PBMCs) and TILs, including T-cell subsets, NK cells, and MDSC.

9. MEASUREMENT OF EFFECT

9.1 Radiographic Response

Response and progression will be evaluated in this study using the Lugano criteria for lymphoma response.²⁵ The response assessment time points are: every 3 cycles during year 1, every 4 cycles during year 2, and every 6 cycles until disease progression. Subjects should have PET/CT at baseline and at time to confirm CR. If an additional CT scan is performed earlier than the specified time points due to changes in the subject's clinical status, please also perform an additional response assessment at that time. Once a subject has progressed, no further response assessments are required.

PET-CT. PET-CT is the preferred imaging modality for baseline assessment, and for CR confirmation.

Conventional CT and MRI. This guideline has defined measurability of lesions on CT scan based on the assumption that CT thickness is 5mm or less. If CT scans have slice thickness greater than

5 mm, the minimum size of a measurable lesion should be twice the slice thickness. MRI is also acceptable in certain situations.

9.1.1 Response Criteria

Response and Site	PET-CT-Based Response	CT-Based Response
Complete	Complete metabolic response	Complete radiologic response (all of the following)
Lymph nodes and extralymphatic sites	
Score 1, 2, or 3* with or without a residual mass on 5PS†
 
It is recognized that in Waldeyer's ring or extranodal sites with high physiologic uptake or with activation within spleen or marrow (e.g., with chemotherapy or myeloid colony-stimulating factors), uptake may be greater than normal mediastinum and/or liver. In this circumstance, complete metabolic response may be inferred if uptake at sites of initial involvement is no greater than surrounding normal tissue even if the tissue has high physiologic uptake
	
Target nodes/nodal masses must regress to ≤ 1.5 cm in LDi
 
No extralymphatic sites of disease

Nonmeasured lesion	Not applicable	Absent
Organ enlargement	Not applicable	Rgress to normal
New lesions	None	None
Bone marrow	No evidence of FDG-avid disease in marrow	Normal by morphology; if indeterminate, IHC negative
Partial	Partial metabolic response	Partial remission (all of the following)
Lymph nodes and extralymphatic sites	Score 4 or 5† with reduced uptake compared with baseline and residual mass(es) of any size	$\geq 50\%$ decrease in SPD of up to 6 target measurable nodes and extranodal sites
	At interim, these findings suggest responding disease	When a lesion is too small to measure on CT, assign 5 mm \times 5 mm as the default value
	At end of treatment, these findings indicate residual disease	When no longer visible, 0 \times 0 mm
		For a node > 5 mm \times 5 mm, but smaller than normal, use actual measurement for calculation
Nonmeasured lesions	Not applicable	Absent/normal, regressed, but no increase
Organ	Not applicable	Spleen must have regressed by $>$

Response and Site	PET-CT-Based Response	CT-Based Response
enlargement		50% in length beyond normal
New lesions	None	None
Bone marrow	Residual uptake higher than uptake in normal marrow but reduced compared with baseline (diffuse uptake compatible with reactive changes from chemotherapy allowed). If there are persistent focal changes in the marrow in the context of a nodal response, consideration should be given to further evaluation with MRI or biopsy or an interval scan	Not applicable
No response or stable disease	No metabolic response	Stable disease
Target nodes/nodal masses, extranodal lesions	Score 4 or 5 with no significant change in FDG uptake from baseline at interim or end of treatment	< 50% decrease from baseline in SPD of up to 6 dominant, measurable nodes and extranodal sites; no criteria for progressive disease are met
Nonmeasured lesions	Not applicable	No increase consistent with progression
Organ enlargement	Not applicable	No increase consistent with progression
New lesions	None	None
Bone marrow	No change from baseline	Not applicable
Progressive disease	Progressive metabolic disease	Progressive disease requires at least 1 of the following
Individual target nodes/nodal masses	Score 4 or 5 with an increase in intensity of uptake from baseline and/or	PPD progression:
Extranodal lesions	New FDG-avid foci consistent with lymphoma at interim or end-of-treatment assessment	An individual node/lesion must be abnormal with: LDi > 1.5 cm and Increase by $\geq 50\%$ from PPD nadir and An increase in LDi or SDi from nadir 0.5 cm for lesions ≤ 2 cm 1.0 cm for lesions > 2 cm In the setting of splenomegaly, the splenic length must increase by $> 50\%$ of the extent of its prior increase beyond baseline (e.g., a 15-cm spleen must increase to > 16 cm). If no prior splenomegaly, must increase by at least 2 cm from

Response and Site	PET-CT-Based Response	CT-Based Response
		baseline New or recurrent splenomegaly
Nonmeasured lesions	None	New or clear progression of preexisting nonmeasured lesions
New lesions	New FDG-avid foci consistent with lymphoma rather than another etiology (e.g., infection, inflammation). If uncertain regarding etiology of new lesions, biopsy or interval scan may be considered	Regrowth of previously resolved lesions A new node > 1.5 cm in any axis A new extranodal site > 1.0 cm in any axis; if < 1.0 cm in any axis, its presence must be unequivocal and must be attributable to lymphoma Assessable disease of any size unequivocally attributable to lymphoma
Bone marrow	New or recurrent FDG-avid foci	New or recurrent involvement

- Abbreviations: 5PS, 5-point scale; CT, computed tomography; FDG, fluorodeoxyglucose; IHC, immunohistochemistry; LDi, longest transverse diameter of a lesion; MRI, magnetic resonance imaging; PET, positron emission tomography; PPD, cross product of the LDi and perpendicular diameter; SDi, shortest axis perpendicular to the LDi; SPD, sum of the product of the perpendicular diameters for multiple lesions.
- * A score of 3 in many patients indicates a good prognosis with standard treatment, especially if at the time of an interim scan. However, in trials involving PET where de-escalation is investigated, it may be preferable to consider a score of 3 as inadequate response (to avoid undertreatment). Measured dominant lesions: Up to six of the largest dominant nodes, nodal masses, and extranodal lesions selected to be clearly measurable in two diameters. Nodes should preferably be from disparate regions of the body and should include, where applicable, mediastinal and retroperitoneal areas. Non-nodal lesions include those in solid organs (e.g., liver, spleen, kidneys, lungs), GI involvement, cutaneous lesions, or those noted on palpation. Nonmeasured lesions: Any disease not selected as measured, dominant disease and truly assessable disease should be considered not measured. These sites include any nodes, nodal masses, and extranodal sites not selected as dominant or measurable or that do not meet the requirements for measurability but are still considered abnormal, as well as truly assessable disease, which is any site of suspected disease that would be difficult to follow quantitatively with measurement, including pleural effusions, ascites, bone lesions, leptomeningeal disease, abdominal masses, and other lesions that cannot be confirmed and followed by imaging. In Waldeyer's ring or in extranodal sites (e.g., GI tract, liver, bone marrow), FDG uptake may be greater than in the mediastinum with complete metabolic response, but should be no higher than surrounding normal physiologic uptake (e.g., with marrow activation as a result of chemotherapy or myeloid growth factors).
- † PET 5PS: 1, no uptake above background; 2, uptake \leq mediastinum; 3, uptake $>$ mediastinum but \leq liver; 4, uptake moderately $>$ liver; 5, uptake markedly higher than liver and/or new lesions; X, new areas of uptake unlikely to be related to lymphoma.

9.1.2 Duration of Response

Duration of overall response: The duration of overall response is measured from the time

measurement criteria are met for CR or PR (whichever is first recorded) until the first date that recurrent or progressive disease is objectively documented (taking as reference for progressive disease the smallest measurements recorded since the treatment started).

Duration of CR: The duration of CR is measured from the time measurement criteria are first met for CR until the first date that recurrent disease is objectively documented.

Duration of stable disease: Stable disease is measured from the start of the treatment until the criteria for progression are met, taking as reference the smallest measurements recorded since the treatment started.

9.1.3 Progression-Free Survival (PFS)

PFS is defined as the duration of time from start of treatment to time of documentation of progression or death from any cause.

9.1.4 Overall Survival (OS)

OS is defined as the duration of time from start of treatment to death from any cause.

9.2 Molecular Response

All subjects will undergo evaluation for molecular evidence of disease in the peripheral blood at baseline, and after cycles 6 and 12 of induction. Subjects that are in at least PR will undergo evaluation of MRD during maintenance, including every 4 cycles during year 2, and every 6 cycles during years 3-5. MRD negative CR is defined as complete remission per Lugano criteria with undetectable MRD ($< 1 \times 10^{-6}$) in peripheral blood using the AdaptiveBiotech Clonoseq assay.

Mantle cell lymphoma MRD

Adaptive Biotechnology ClonoSeq assay will be used to detect MRD in MCL during induction and maintenance. In addition, Clonoseq assay will be used to guide treatment intensity and duration during maintenance for patients achieving MRD negative CR as discussed in Section 5.1.

10. DATA REPORTING / REGULATORY CONSIDERATIONS

10.1 Data Collection

REDCap will be used to capture all treatment, toxicity, efficacy, and adverse event data for all enrolled patients.

REDCap (Research Electronic Data Capture) is a free data management software system that is fully supported by the Weill-Cornell Medical Center CTSC. It is a tool for the creation of customized, secure data management systems that include Web-based data-entry forms, reporting

tools, and a full array of security features including user and group based privileges, authentication using institution LDAP system, with a full audit trail of data manipulation and export procedures. REDCap is maintained on CTSC-owned servers that are backed up nightly and support encrypted (SSL-based) connections. Nationally, the software is developed, enhanced and supported through a multi-institutional consortium led by the Vanderbilt University CTSA.

10.2 Regulatory Considerations

All protocol amendments and consent form modifications will be made by the Principal Investigator. Acerta and Celgene will have the opportunity to review and approve the changes prior to submission of these changes to the local IRB and distribution to participating sites.

11. STATISTICAL CONSIDERATIONS

11.1 Study Design

This is an exploratory phase II study with a safety run-in period to evaluate the preliminary evidence of efficacy and safety of the combination of acalabrutinib, lenalidomide and rituximab (ALR) in previously untreated mantle cell lymphoma. If the data from this trial provide evidence of efficacy in this patient population, the treatment will be considered for further investigation. A total of 28 patients (24 eligible and evaluable patients, including the patients from the safety run-in period) will be enrolled in the ALR cohort.

We plan to expand the study to include a new cohort of 10 MCL patients who will receive treatment with the acalabrutinib, lenalidomide and Obinutuzumab (ALO) regimen. The new cohort will contribute to the analysis of safety and feasibility secondary endpoints.

The ALO regimen will be considered feasible if all of the following conditions are met:

- No more than 2 of the first 6 evaluable subjects experiencing potentially drug-related excess toxicities during safety run-in observation, which is defined as 28 days of cycle 1 of treatment.
- No more than 2/10 patients stop treatment during the first year due to adverse events.

11.2 Sample Size

The primary endpoint for this study is MRD-negative CR (defined as MRD in peripheral blood $<10^{-6}$) at the conclusion of 12 cycles of ALR induction therapy. We project to achieve at least 20% of absolute CR improvement with the ALR triplet from a historical CR of 60% with the lenalidomide plus rituximab doublet. The sample size required to estimate this improvement is 24, by an exact binomial test assuming an alpha level of 0.1 and power of 80%. Additional 4 patients will be enrolled to account for potential attrition so a total of 28 patients will be enrolled in the ALR cohort. We also plan to enroll 10 patients to the ALO feasibility cohort. Formal justification of the sample size for feasibility cohort is not required. In total, 38 patients will be enrolled in the study.

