2. BACKGROUND

2.1 Mantle Cell Lymphoma

Mantle cell lymphoma (MCL) is an incurable lymphoma with a median survival of 5-7 years. Standard front-line treatment usually includes chemoimmunotherapy and often involves aggressive approaches, yet most patients continue to relapse despite intensive therapy. The major therapeutic goals in patients with MCL are to prolong survival and improve quality of life. The unmet needs in MCL management in the frontline setting are to develop approaches that can be targeted to the appropriate patients based on disease biology, are well tolerated and accessible by

all patients, and can be administered in the outpatient community¹.

Over the past decade, four non-chemotherapy options, namely bortezomib, lenalidomide, ibrutinib, and most recently acalabrutinib, have been approved by the United States Food and Drug Administration for treatment of MCL²⁻⁵. Continuous therapy with BTK inhibitors in particular have shown impressive clinical activity with generally favorable toxicity profile in relapse/refractory setting. The introduction of novel agents corresponds with better outcomes in population studies, suggesting that the availability of new options that can be used sequentially may be extending survival. Furthermore, emerging data with novel agents and combinations is poised to challenge the conventional chemotherapy-based treatment paradigm in frontline setting, making effective and less toxic “chemo-free” treatment accessible to most MCL patients a tangible reality.

Recently published data from Weill Cornell Medicine (WCM) have shown that the combination of lenalidomide plus rituximab administered until progression is active and well tolerated as front-line therapy in patients with MCL with a complete response (CR) rate of 61%, a 2-year progression-free survival (PFS) of 85% and a 4-year PFS of 70%, demonstrating the feasibility of administering novel agents as effective induction and chronic maintenance therapy in the outpatient setting⁶. MRD status was sampled during long-term follow-up, and 6 of 7 patients with available samples achieved MRD negativity⁷, providing the first proof-of-concept evidence that lenalidomide-based novel agent/combination have the potential to achieve MRD-negative remission. The apparent activity of the regimen warrants further evaluation, but attempts at improving the efficacy and tolerability as well as efforts to better define the patient subsets that might benefit most are also needed.

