BCR signaling is necessary to sustain the viability of B cell malignancies via constitutive activation of NF-κB pathway. An antigen-driven origin of mantle cell lymphoma has been suggested whereby BCR activation contributes to proliferative signature of MCL lymphomagenesis ¹⁹. BTK inhibitors provide therapeutic activity by blocking chronic BCR signaling leading to a decrease in NF-κB activity. Lenalidomide downmodulates IRF4, leading to an increase in IFNβ secretion and a decrease in NF-κB activity ²⁰. Combining BTK inhibitor and lenalidomide therefore appears to target key pathways in MCL which may increase therapeutic synergy and reduce overall resistance development. Additionally, combining acalabrutinib with lenalidomide + R may have theoretic advantage over ibrutinib with lenalidomide + R, given minimal impact of acalabrutinib on activation and expansion of NK/T cells compared to ibrutinib ²¹, which potentially preserves immunomodulatory amplification of lenalidomide on rituximab-induced ADCC.

The feasibility of the triple combination of BTK inhibitor + lenalidomide + rituximab in MCL has been demonstrated by the Nordic PHILEMON study which uses lenalidomide at 15 mg po daily, days 1-21, Ibrutinib 560 mg po days 1-28, and standard dose rituximab ¹⁵. Furthermore, the triple combination was experimented in a phase 1 FL frontline study and a phase I/II R/R DLBCL study. Phase 2 recommended dose was lenalidomide at 20 mg daily, days 1-21, and ibrutinib at 560 mg daily in 28-day cycle for both studies ¹⁶. Given the generally similar and well-tolerated profile of acalabrutinib and ibrutinib, we expect similar safety profile with the acalabrutinib, lenalidomide and rituximab combination in frontline MCL treatment. Because relapsed/refractory MCL has been associated with poor outcomes, every study to evaluate lenalidomide or BTK inhibitors to date, including the Nordic PHILEMON study, treatment has continued until disease progression.

Based on the relatively high clinical CR rate with frontline R2 regimen (CR 60%), and frontline IR regimen (CR 80%), we hypothesize that addition of BTK inhibitor acalabrutinib to R2 regimen would further synergize clinical activity of either agent and improve MRD negative CR rate from 60% to a target rate of 80%. The improvement in MRD CR rate would facilitate

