11.3 Analysis Plan for Endpoints

11.3.1 Primary Endpoints

The primary endpoint of CR will be calculated, and a 90% Clopper-Pearson confidence interval will be estimated via exact binomial proportions.

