11.3.3 Correlative Endpoints

The frequency of subjects experiencing adverse event will be tabulated. Paired t-test will be performed to assess the differences between baseline and the end of treatment for numerical variables, such as gene expression, immunophenotypic changes, cfDNA, etc. All p-values will be two-sided with statistical significance evaluated at the 0.1 alpha level. Ninety percent confidence intervals will be calculated to assess the precision of the obtained estimates. All analyses will be performed in SAS Version 9.4 (SAS Institute, Inc., Cary, NC).

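### Section 11.2 sizes the ALR cohort for a one-sided 0.10 exact test, but the only primary analysis in 11.3.1 is a two-sided 90% interval

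*Combined protocol and SAP*

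**What the plan says.** Section 11.2 states that "The primary endpoint for this study is MRD-negative CR" after 12 cycles of ALR induction. It projects a gain of at least 20 percentage points "from a historical CR of 60% with the lenalidomide plus rituximab doublet", and gives the number needed as "24, by an exact binomial test assuming an alpha level of 0.1 and power of 80" percent. Four more patients are added for attrition, so 28 are enrolled. The section does not say whether the test is one- or two-sided, and it gives no response count for success.

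Section 11.3.1 is the whole primary analysis. The rate is calculated and "a 90% Clopper-Pearson confidence interval will be estimated via exact binomial proportions". It mentions no test, no comparison with 60% and no threshold.

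Section 11.1 links the result to the next step only in general terms: "If the data from this trial provide evidence of efficacy in this patient population, the treatment will be considered for further investigation".

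The one statement about sidedness in section 11 is in 11.3.3, under Correlative Endpoints: "All p-values will be two-sided with statistical significance evaluated at the 0.1 alpha level".

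**The concern.** The alpha and power in 11.2 belong to a particular test. The analysis section does not perform it, and plans an interval whose tails are half as large as that test's alpha. A reader who checks whether the reported interval excludes 60% is applying a stricter rule than the one used to size the trial, with less power than 11.2 states.

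What is at stake is how a borderline result is read. At the sizing test's own cut-off, the test indicates improvement over 60% while the planned interval still includes 60%. Unless the plan says beforehand which of the two answers the question in 11.1, the choice could be made after the count is known.

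**Working it through.** **Inputs.** Null rate 0.60, alternative 0.60 + 0.20 = 0.80, alpha 0.10, power 80%, exact binomial test, n = 24 (all 11.2). The 90% Clopper-Pearson interval is from 11.3.1. Evaluable numbers above 24 are possible because 28 are enrolled (11.1, 11.2).

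**Reproducing n = 24.** The cut-off r is the smallest count with P(X ≥ r | n, 0.60) ≤ the upper-tail level. Power is P(X ≥ r | n, 0.80).

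- One-sided 0.10, n = 24: P(X ≥ 17 | 0.60) = 0.192, too large; P(X ≥ 18 | 0.60) = 0.096, so r = 18. Power = P(X ≥ 18 | 0.80) = 81.1%. In a scan from n = 15 upward, 24 is the first n to reach 80%. The plan's figure is therefore reproduced.
- Two-sided 0.10 (0.05 in the upper tail), n = 24: P(X ≥ 18 | 0.60) = 0.096, too large; P(X ≥ 19 | 0.60) = 0.040, so r = 19. Power = P(X ≥ 19 | 0.80) = 65.6%. The first n in the scan to reach 80% is 36.
- Normal-approximation check: n = [(z₁·√0.24 + z₀.₈₀·√0.16) / 0.20]², where z₁ is the normal quantile for the upper-tail level. This gives 23.3 one-sided and 32.6 two-sided.

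Of these two versions, only the one-sided test gives 24.

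**Reading the planned interval against 60%.** The lower limit at count r is the 0.05 quantile of Beta(r, n − r + 1). It exceeds 0.60 exactly when P(X ≥ r | 0.60) < 0.05, so this rule has the two-sided test's cut-off.

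- 18/24 (75.0%): 90% interval 56.5% to 88.5%, which includes 60%; one-sided p = 0.096.
- 19/24 (79.2%): 90% interval 61.1% to 91.4%, which excludes 60%; one-sided p = 0.040.

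The bound that matches the sizing test is the one-sided 90% lower limit, the 0.10 quantile of the same beta distribution. At 18/24 it is 60.2%, which agrees with the test.

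**How often the two readings differ.** At n = 24 they differ only at 18.

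- True rate 80%: 0.8111 − 0.6559 = 0.155, about 16%.
- True rate 60%: 0.0960 − 0.0400 = 0.056, about 6%.

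**If more than 24 are evaluable:**

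| Evaluable n | One-sided 0.10 cut-off | Actual alpha | Power | Cut-off if 90% interval must exclude 60% | Power |
|---|---|---|---|---|---|
| 24 | 18 | 0.096 | 81.1% | 19 | 65.6% |
| 25 | 19 | 0.074 | 78.0% | 20 | 61.7% |
| 26 | 20 | 0.056 | 74.7% | 21 | 57.7% |
| 27 | 20 | 0.095 | 84.4% | 21 | 71.3% |
| 28 | 21 | 0.074 | 81.8% | 22 | 67.8% |

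At every n the two cut-offs are one count apart. One-sided power falls below 80% at 25 and 26 because the binomial is discrete.

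**The case against.** The strongest reply is that 11.2 already contains the rule. It names the test, the reference rate, the gain, alpha and power; only the one-sided version gives 24; and those inputs fix the cut-off at 18. The wording about improvement is directional. The interval can fairly be taken as descriptive, since 11.3.2 uses 90% intervals for PFS, OS and time to next treatment, and 11.3.3 uses them to show precision. The trial calls itself exploratory, 11.1 promises only consideration of further work, and the disagreement is one count.

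Most of this stands, and it rules out three stronger readings that a reader might infer:

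- That the plan has no primary decision rule. The rule can be derived from 11.2; it is just not written out.
- That the trial really has 65.6% power, or should have been larger. That requires the interval to be the success criterion, and no passage makes it one.
- That the two-sided sentence in 11.3.3 governs the primary endpoint. It sits under Correlative Endpoints, directly after the paired t-test, and 11.3.1 produces no p-value. Its scope is unclear at most.

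The reply does not remove the mismatch. The 80% power attaches to a test that the primary analysis section does not carry out. The interval planned there has a different tail level, and 11.3.1 does not call it descriptive.

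**Conclusion.** The concern holds as a mismatch between sizing and analysis. The sample size of 24 is correct for a one-sided exact test at 0.10 with success at 18 or more of 24 (actual alpha 0.096, power 81.1%). The only inference planned for the primary endpoint is a two-sided 90% interval. Read against 60%, that interval would require 19 of 24, with power 65.6%, about 15 points lower (81.1 − 65.6 = 15.5).

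The reach is narrow: one count at n = 24, with about a 16% chance if the true rate is 80% and 6% if it is 60%, in an exploratory trial. It is still worth correcting, because the change is small and settles what the trial can conclude at that count.

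All figures take 60% as the null and 80% as the alternative. Section 11.2 describes the 60% as a historical CR rate, whereas 2.3 speaks of a plan to "improve MRD negative CR rate from 60% to a target rate of 80" percent. For the doublet, 2.1 reports MRD only as "6 of 7 patients with available samples achieved MRD negativity". Whether 60% is the right null for MRD-negative CR is a separate point; if it changed, the cut-offs here would have to be recalculated.

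**What to change.** Preferred, because it keeps the sample size, alpha and power in 11.2:

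- In 11.2, state that the test is one-sided (null 60%, alternative 80%, alpha 0.10), with success at 18 or more of 24, actual alpha 0.096 and power 81.1%. Add the cut-offs for 25, 26, 27 and 28 evaluable patients: 19, 20, 20 and 21, with power 78.0%, 74.7%, 84.4% and 81.8%.
- In 11.3.1, name this test as the primary analysis, report the matching one-sided 90% lower bound (60.2% at 18/24), and label the two-sided 90% interval descriptive.
- In 11.3.3, limit the sentence on two-sided p-values to the correlative analyses.

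Alternative: if the sponsor intends the 90% interval to decide, say so in 11.3.1, give the cut-off of 19 of 24, and restate power in 11.2 as 65.6% at n = 24.

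Either choice should be fixed before the primary result is examined. The Protocol Summary gives accrual as July 2019 to July 2022, and the documents do not say whether ALR outcomes are already known. If they are, the amendment should say so, because the choice would then be post hoc.

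The cost is wording in two or three subsections and no extra patients. The downside is either an openly one-sided 10% test, with power below 80% at 25 or 26 evaluable patients, or a lower stated power.
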